## 2 ELIGIBILITY ASSESSMENT AND ENROLLMENT

### 2.1 ELIGIBILITY CRITERIA

#### 2.1.1 Inclusion Criteria

2.1.1.1 Patients must have a confirmed histologic diagnosis of an indolent CD20 positive B-cell lymphoma according to the criteria established by the 2016 version of the World Health Organization (WHO) classification system. Lymphomas with any prior CD20 expression (by immunohistochemistry or flow cytometry) will be considered eligible. Diagnosis must be confirmed by Laboratory of Pathology, NCI and the following indolent B-cell lymphomas are included:

- Follicular lymphoma (FL): must be grade 1-2 or 3a
- Marginal zone lymphoma (MZL)
- Mantle cell lymphoma (MCL)
- Chronic lymphocytic leukemia (CLL)

2.1.1.2 Participant must have relapsed and/or refractory disease, as defined below:

- FL: relapsed after and/or refractory to at least two (2) prior lines of therapy with at least one of those therapies containing an anti-CD20 monoclonal antibody.

**NOTE:** Participants with FL may be eligible after one (1) prior line of therapy if they have either:

- Follicular lymphoma international prognostic index (FLIPI)  $\geq 2$  ([120](#))
- Disease progression within 24 months of the end of last therapy (POD24)

- MZL: relapsed after and/or refractory to at least two (2) prior lines of therapy, with at least one containing an anti-CD20 monoclonal antibody.
- MCL: relapsed after and/or refractory to at least two (2) prior lines of therapy, with at least one containing an anti-CD20 monoclonal antibody.

**NOTE:** Participants with MCL may be eligible after one (1) prior line of therapy if they have either:

- Blastoid or pleomorphic histology
- 17p deletion
- *TP53* mutation or deletion
- Ki67  $\geq 30\%$
- Received a BTK inhibitor as first line therapy

- CLL: relapsed after and/or refractory to at least two (2) prior lines of therapy. Participants with CLL are not required to have had therapy containing anti-CD20.

**NOTE:** Participants with CLL may be eligible after one (1) prior line of therapy if they have either:

- 17p deletion
- *TP53* mutation or deletion
- Received both a Bruton's Tyrosine Kinase (BTK) inhibitor AND a B-cell

lymphoma 2 (BCL2) inhibitor as first line therapy

**NOTE:** Participants must not have received prior treatment with a CD47 or SIRP $\alpha$  targeting agent.

2.1.1.3 Adequate tissue from diagnostic biopsy (archival or fresh) must be available for performance of correlative studies

**NOTE:** Tumor tissue may be from any previously collected tissue and adequacy is at the discretion of the Principal Investigator. If prior tissue is not available, patient must be willing to undergo baseline tissue biopsy (for patients with known or suspected bone marrow involvement, bone marrow may be acceptable tissue per discretion of the investigator).

2.1.1.4 Patients must have at least evaluable disease as assessed by clinical exam (i.e., palpable lymphadenopathy, measurable skin lesions, etc.), laboratory assessment (i.e., lymphoma involvement of bone marrow or peripheral blood by morphology, cytology or flow cytometry), and/or imaging (measurable lymph nodes or masses on CT or MRI and/or evaluable FDG-avid lesions on PET). Patients may also have measurable disease.

**NOTE:** Patients with known active CNS lymphoma are not eligible.

2.1.1.5 Age  $\geq$ 18 years

**NOTE:** Because no dosing or adverse event data are currently available on the use of magrolimab in patients  $<$ 18 years of age, children are excluded from this study

2.1.1.6 ECOG performance status  $\leq$  2 (see [Appendix A](#))

2.1.1.7 Adequate organ function as evidenced by the following laboratory parameters:

|   |   |
|---|---|
| Absolute neutrophil count (ANC)                                     | $\geq 1,000 / \text{mm}^3$  |
| Platelets   | $\geq 50,000 / \text{mcL}$ (transfusions permitted)   |
| Hemoglobin  | $\geq 9 \text{ g/dL}$ (transfusions permitted). NOTE: Patients must have required fewer than 2 units of RBC transfusion in the 4 weeks prior to screening. Additional transfusions after screening and prior to enrollment are acceptable. |
| Renal function  | Glomerular filtration rate (GFR) $\geq 30 \text{ mL/min/1.73 m}^2$ as estimated by the Modification of Diet in Renal Disease (MDRD) abbreviated formula. If not on target, a 24-hour urine creatinine clearance can be used to directly measure.  |
| Aspartate aminotransferase (AST) and alanine aminotransferase (ALT) | $\leq 3.0 \times$ the upper ULN

NOTE: Patients with liver involvement with lymphoma $\leq 5.0 \times$ ULN   |
| Bilirubin   | $\leq 1.5 \times$ ULN

NOTE: Patients with Gilbert's syndrome may have a bilirubin level $> 1.5 \times$ ULN, per discretion of the investigator  |

2.1.1.8 The effects of the study drugs on the developing human fetus are unknown. For this

reason, women of childbearing potential (WOCBP) and men must agree to use effective contraception when sexually active. This applies for the time period between signing of the informed consent form and for the following time frames after the last dose of drug, whichever is later: 90 days after the last dose of magrolimab, 30 days after the last dose of venetoclax, and 18 months after the last dose of obinutuzumab for women and 6 months after the last dose of obinutuzumab for men. Men should refrain also from donating sperm for these same timeframes, and women must also refrain from donating eggs.

**NOTE:** WOCBP is defined as any female who has experienced menarche and who has not undergone successful surgical sterilization or who is not postmenopausal (i.e., amenorrheic for >12 months without alternative medical cause; post-menopausal status in females under 55 years of age should be confirmed with a serum follicle-stimulating hormone [FSH] level within applicable local laboratory reference range for postmenopausal women). Permanent sterilization methods include but are not limited to hysterectomy, bilateral salpingectomy and bilateral oophorectomy. The investigator or a designated associate is requested to advise the patient how to achieve highly effective birth control (failure rate of less than 1%), e.g., intrauterine device (IUD), intrauterine hormone-releasing system (IUS), bilateral tubal occlusion, vasectomized partner and sexual abstinence. The use of condoms by male patients is required unless the female partner is permanently sterile. See **Appendix B** for complete details of acceptable contraceptive methods.

- 2.1.1.9 Ability of patient to understand and the willingness to sign a written informed consent document
- 2.1.1.10 Patients with prior autologous or allogeneic stem cell transplantation are potentially eligible if transplanted > 6 months ago, and no active graft-vs-host disease requiring immunosuppressants.

## **2.1.2 Exclusion Criteria**

- 2.1.2.1 Concomitant use of any investigational anti-lymphoma treatment
- 2.1.2.2 Known primary or acquired immunodeficiency syndrome (e.g., HIV) or known infection with human T-cell leukemia virus 1 (HTLV1). **NOTE:** HIV-positive patients on combination antiretroviral therapy are ineligible because of the potential for pharmacokinetic interactions with the study drugs. In addition, these patients are at increased risk of lethal infections when treated with marrow-suppressive therapy. In the future, appropriate studies will be undertaken in patients receiving combination antiretroviral therapy when indicated.
- 2.1.2.3 History of hemolytic anemia or autoimmune thrombocytopenia in the 3 months prior to enrollment. Patients with positive Direct Agglutination Test (DAT) but no evidence of clinically active hemolysis are eligible.
- 2.1.2.4 Hepatitis B surface antigen or hepatitis B DNA PCR positive. **NOTE:** Subjects who are hepatitis B core antibody positive will need to have a negative HBV DNA PCR result before enrollment. Those with a positive PCR for hepatitis B are excluded.
- 2.1.2.5 Pregnant or breastfeeding patients. **NOTE:** Pregnant women are excluded in this study because of the potential for teratogenic or abortifacient effects. Because there is an

unknown but potential risk for adverse events in nursing infants secondary to treatment of the mother with the study drugs, breastfeeding should be discontinued.

2.1.2.6 Requirement to continue on any of the medications that have significant potential for drug-drug interactions with the study regimen, as indicated in Section 4.2. For example, the following:

- Use of strong CYP3A inhibitors 7 days prior to or at initiation of venetoclax, and during ramp-up phase is contraindicated in patients with MZL, CLL and MCL (see Sections 4.2.1, 4.2.1.2, and Appendix C, also see Section 4). For FL patients, use of strong CYP3A inhibitors is contraindicated 7 days prior to and during the first two weeks of venetoclax treatment.
- Consumption of one or more of the following within 3 days prior to the first dose of any study drug:
  - Grapefruit or grapefruit products
  - Seville oranges including marmalade containing Seville oranges
  - Star fruit

2.1.2.7 Uncontrolled intercurrent illness including, but not limited to the following that may limit interpretation of results or that could increase risk to the patient at the discretion of the investigator:

- Active hepatitis C infection. **NOTE:** Subjects who are hepatitis C antibody positive will need to have a negative HCV PCR result before enrollment. Those with a positive PCR for hepatitis C are excluded.
- Any second malignancy that requires active systemic therapy
- Known mental or physical illness that would interfere with cooperation with the requirements of the trial or confound the results or interpretation of the results of the trial and, in the opinion of the treating investigator, would make the patient inappropriate for entry into the study
- Known active infection, or any major infection requiring treatment with IV antibiotics or hospitalization within 4 weeks prior to commencement of the study treatment.

2.1.2.8 Vaccination with a live vaccine  $\leq$ 28 days prior to commencement of the study treatment.

2.1.2.9 Inability or unwillingness to swallow a large number of tablets.

2.1.2.10 Known hypersensitivity to any of the study medications or their excipients.

2.1.2.11 History of inflammatory bowel disease (e.g., Crohn's disease or ulcerative colitis).

2.1.2.12 History of malabsorption syndrome felt to be significant enough to interfere with enteral absorption at the discretion of the investigator.

### **2.1.3 Recruitment Strategies**

Study participants will be recruited from the population of patients screened in the lymphoid malignancies' clinic of the National Institutes of Health. Our research team currently has an active protocol to study the clonal evolution in FL that enrolls patients with untreated FL who are

appropriate for observation as well as those who require immediate treatment. In addition, we participate in a locoregional consortium of eight academic institutions within the Mid-Atlantic region (Mid-Atlantic Lymphoma Research Consortium) that shares information regarding active clinical protocols and aims to enhance patient recruitment across the region. Our patients for this study will therefore consist of those from the FL clonal evolution study, referrals from outside physicians, and patient self-referrals.

This protocol may also be abstracted into a plain language announcement posted on NIH websites ([ccr.cancer.gov/](http://ccr.cancer.gov/) Lymphoid-Malignancies-Branch, [ClinicalTrials.gov](http://ClinicalTrials.gov)) and on NIH social media platforms.

## **2.2 SCREENING EVALUATION**

### **2.2.1 Screening activities performed prior to obtaining informed consent**

Minimal risk activities that may be performed before the subject has signed a consent include the following:

- Email, written, in person or telephone communications with prospective subjects
- Review of existing medical records to include H&P, laboratory studies, etc.
- Review of existing MRI, x-ray, or CT images
- Review of existing photographs or videos
- Review of existing pathology specimens/reports from a specimen obtained for diagnostic purposes

### **2.2.2 Screening activities performed after a consent for screening has been signed**

The following activities will be performed only after the subject has signed the study consent OR the consent for study 01C0129 (provided the procedure is permitted on that study), on which screening activities will be performed. Assessments performed at outside facilities or on another NIH protocol within the timeframes below may also be used to determine eligibility once a patient has signed the consent, unless otherwise noted.

**NOTE:** Assessments and procedures to confirm study eligibility should be completed within 28 days prior to the start of treatment (unless otherwise noted). See also the Study Calendar ([Appendix G](#)).

### **2.2.3 Clinical Evaluations**

- Disease history, including: diagnosis, prior chemotherapy and/or radiation treatment (if applicable), and significant prior/ongoing side effects and symptoms
- Complete medical history, including: all active conditions considered to be clinically significant by the treating investigator
- Physical examination, including: height (screening only), weight, vital signs (i.e., temperature, pulse, respiratory rate, and blood pressure); review of concomitant medications and symptoms/side effects; and, assessment of performance status using the ECOG scale

### **2.2.4 Laboratory Evaluations**

**NOTE:** Results from outside NIH are accepted.

- CBC with differential
- Chemistry panels (as noted) or specific analyte required for eligibility, including: Creatinine (i.e., or Acute Care Panel/Basic Metabolic Panel); ALT, AST, total and direct (if required) bilirubin (i.e., or Hepatic Panel/Liver Function Panel); and 24-hour urine creatinine clearance (if needed to measure CrCl)
- Coagulation panel: PT/INR and aPTT
- LDH
- Urinalysis
- Hepatitis B surface antigen (HBsAg), Hepatitis B core antibody, Hepatitis C antibody (HCV) [qualitative]) (within 3 months allowed)
- HIV antibody (within 3 months allowed)
- Urine and/or serum HCG in women of childbearing potential (within 7 days prior to initiation of study therapy)
- Direct Anti-Globulin Test (DAT)
- Assessment of 17p deletion by karyotyping of blood, bone marrow, or tissue sample (results from outside of NIH and/or prior to the 28-day screening window are accepted)

## **2.2.5 Imaging Studies**

**NOTE:** Results from NIH only.

- CT chest, abdomen and pelvis or MRI

## **2.2.6 Other Procedures to be performed/samples to be collected**

- Pathologic review/confirmation of diagnosis by Laboratory of Pathology, NCI (no time limit). A tissue sample is required for this evaluation; if archival sample is not available, a fresh tumor or bone marrow biopsy will be obtained.
- Bone marrow aspiration with flow cytometry and biopsy within 12 months prior to starting treatment, unless repeat at screening/baseline felt to be clinically indicated in the opinion of the investigator (results from outside NIH are accepted; flow cytometry not required in these cases).
- Flow cytometry will be performed on peripheral blood for both diagnostic and staging purposes (only NIH results accepted; NCI Laboratory of Pathology)

## **2.3 PARTICIPANT REGISTRATION AND STATUS UPDATE PROCEDURES**

Registration and status updates (e.g., when a participant is taken off protocol therapy and when a participant is taken off-study) will take place per CCR SOP ADCR-2, CCR Participant Registration & Status Updates found at:

<https://ccrod.cancer.gov/confluence/pages/viewpage.action?pageId=73203825>.

### **2.3.1 Screen Failures**

Screen failures are defined as participants who consent to participate in the clinical trial but are not subsequently assigned to the study intervention or entered in the study. A minimal set of screen failure information is required to ensure transparent reporting of screen failure participants, to meet the Consolidated Standards of Reporting Trials (CONSORT) publishing requirements and to

respond to queries from regulatory authorities. Minimal information includes demography, screen failure details, eligibility criteria, and any serious adverse event (SAE).

### **2.3.2 Treatment Assignment Procedures**

**NOTE:** For NCI CCR registration purposes only.

#### **2.3.2.1 Cohorts**

| Number | Name   | Description  |
|---------------|---|---|
| 1             | Dose-finding:
Relapsed/refractory FL                   | Patients with relapsed or refractory FL
(a minimum of 6 patients; up to 12 patients)               |
| 2             | Dose-finding:
Relapsed/refractory MZL,
MCL, and CLL | Patients with relapsed or refractory MZL, MCL and CLL
(a minimum of 6 patients; up to 12 patients) |
| 3             | Dose-expansion:
Relapsed/refractory FL                 | Patients with relapsed or refractory FL
(up to 18 patients)  |
| 4             | Dose-expansion:
Relapsed/refractory MZL                | Patients with relapsed or refractory MZL
(up to 6 patients)  |
| 5             | Dose-expansion:
Relapsed/refractory MCL                | Patients with relapsed or refractory MCL
(up to 12 patients)                                       |
| 6             | Dose-expansion:
Relapsed/refractory CLL                | Patients with relapsed or refractory CLL
(up to 6 patients)  |

#### **2.3.2.2 Arms**

| Number | Name   | Description  |
|---------------|---|---|
| 1             | Experimental treatment:
FL Dose-finding                | Magrolimab IV with a 1 mg/kg priming dose followed by 30mg/kg loading and maintenance doses + obinutuzumab IV 1000mg + venetoclax 800mg PO combination administered to 6 patients for six (6) cycles (28-days each, Cycles 1-6); further treatment with additional cycles will be response-adapted. Note: DLT assessment of the magrolimab + obinutuzumab + venetoclax triplet will take place during Cycle 1. If $\geq 2$ patients experience DLT, an additional 6 patients will be enrolled at DL(-1) of venetoclax 600mg with magrolimab and obinutuzumab.   |
| 2             | Experimental treatment:
MZL, MCL, and CLL Dose-finding | Magrolimab IV with a 1 mg/kg priming dose followed by 30mg/kg loading and maintenance doses + obinutuzumab IV 1000mg + venetoclax ramp-up to target dose of 400mg over 5 weeks (35 days, Cycle 1) administered to 6 patients. Triplet combination of magrolimab + obinutuzumab + venetoclax (target dose, no ramp-up) will continue for five (5) additional cycles (28-days each, Cycles 2-6); further treatment with additional cycles will be response-adapted. Note: DLT assessment of the magrolimab + obinutuzumab + venetoclax triplet will take place during Cycle 1. If $\geq 2$ patients experience DLT, an additional 6 patients will be enrolled at DL(-1) of venetoclax 200mg with magrolimab and obinutuzumab. |

| Number | Name  | Description  |
|--------|---|--|
| 3      | Experimental treatment:
FL Dose expansion            | Window of magrolimab IV with a 1 mg/kg priming dose followed by 30mg/kg loading and maintenance doses + obinutuzumab IV 1000mg combination for two (2) cycles (28-days each, Cycles -2 and -1), then venetoclax will be added at target dose (dose determined from Arm 1). Triplet combination treatment with magrolimab + obinutuzumab + venetoclax will be 6 cycles (28-days each, Cycles 1-6); further treatment will be response-adapted.  |
| 4      | Experimental treatment:
MZL, MCL, CLL Dose expansion | Window of magrolimab IV with a 1 mg/kg priming dose followed by 30mg/kg loading and maintenance doses + obinutuzumab IV 1000mg combination for two (2) cycles (28-day cycles, Cycles -2 and -1), then venetoclax safety ramp-up to target dose (dose determined from Arm 2) over 5 weeks (35-days, Cycle 1). Triplet combination treatment with magrolimab + obinutuzumab + venetoclax (target dose, no ramp-up) will continue for 5 additional cycles (28-days each, Cycles 2-6); further treatment will be response-adapted. |

### 2.3.2.3 Arm Assignment

This is a four arm, non-randomized study. All patients will receive experimental treatment. During the dose-finding portion, patients in Cohort 1 will be assigned to Arm 1; patients in Cohort 2 will be assigned to Arm 2.

During the dose-expansion portion, patients in Cohort 3 will be assigned to Arm 3; Cohorts 4, 5 and 6 will be assigned to Arm 4.

## 2.4 BASELINE EVALUATION

The baseline evaluations should be performed within 28 days prior to the first dose of magrolimab, unless otherwise noted; tests performed as part of screening do not need to be repeated if they were performed within the specified window. See the Study Calendar ([Appendix G](#)) for details.

## 3 STUDY IMPLEMENTATION

### 3.1 STUDY DESIGN

This is a non-randomized, open-label, four arm, single institution phase 1 study of magrolimab, obinutuzumab, and venetoclax for patients with relapsed/refractory indolent B-cell malignancies. The study involves a novel design that includes a treatment window with a doublet in order to maximize the potential for translational research as well as a safety period to assess the safety of the triplet combination of venetoclax added to magrolimab with obinutuzumab in different disease sub-types.

Research biopsies of lymph nodes and/or bone marrow will be collected at baseline, during the window period treatment with magrolimab + obinutuzumab, and at the time of disease progression.

#### 3.1.1 Dose-Finding Phase

The dose-finding phase will assess the safety of venetoclax when added to obinutuzumab and magrolimab. Up to 6 FL patients in Arm 1 will be treated and undergo DLT assessment during the first 4 weeks (Cycle 1) of triplet combination therapy with magrolimab, obinutuzumab and venetoclax. Venetoclax will be administered at DL1 without a safety ramp-up ([Figure 3](#)). If  $\geq$

patients experience DLT at DL1, up to 6 additional patients will be enrolled (Cohort 1, Arm 1) and treated at DL(-1) of venetoclax. Dose-finding will follow the rules mentioned in **Table 8**.

Up to 6 MZL, MCL or CLL patients treated in Arm 2 will undergo DLT assessment during the first 5 weeks of triplet combination therapy (Cycle 1). Venetoclax will be administered with a safety ramp-up to target dose (dose level 1) (**Table 10, Figure 4**). If  $\geq 2$  patients experience a DLT at DL1, up to 6 additional patients will be enrolled (Cohort 2, Arm 2) and treated at DL (-1) of venetoclax (**Figure 3**). Dose-finding will follow the rules mentioned in **Table 8**.

No more than 2 patients can be in a DLT assessment period at any given time. If a DLT has occurred, only 1 patient can be in the respective DLT assessment period at a given time. Patients who withdraw before completing DLT assessment for reasons other than a DLT, will not be evaluable for assessment of DLT for dose review decisions, and will be replaced.

After completion of the DLT evaluation as above, all patients will be treated with an additional 5, 4-week cycles of triplet combination therapy (magrolimab and obinutuzumab and venetoclax). Final duration of therapy will be based on response to the first 6 cycles of triplet combination therapy. FL, MZL and MCL patients who achieve a CR and CLL patients who achieve a CR with undetectable peripheral blood MRD by flow cytometry after 6 cycles of triplet combination therapy will stop treatment but remain potentially eligible for an additional 6 cycles upon disease relapse provided that they still meet re-treatment criteria and the duration of CR is  $\geq 6$  months. Disease relapse is defined by conventional criteria for clinical relapse that is associated with radiographic progression. Additionally, for CLL patients, positive flow cytometry during follow-up will be considered relapsed for re-treatment. Reappearance of ctDNA is not considered disease relapse on this protocol. Patients who achieve a PR after 6 cycles of triplet combination therapy will be eligible for an immediate additional 6 cycles, and then will stop treatment.

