**Table 8: Venetoclax dose-finding rules for Arms 1 and 2**

| Number of Patients with DLT at a Given Dose Level | Dose-Finding/Dose Decision Rules   |
|---|--|
| <2 out of 6                                       | This target dose will be used in expansion phase   |
| $\geq 2$ out of 6 at DL1                          | Six (6) patients will be entered at dose level (-1).   |
| $\geq 2$ out of 6 at DL (-1)                      | Further enrollment will be stopped, and a safety analysis will be performed to determine further course of action. |

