**Figure 3: Arm 1: FL Dose-finding**

**Figure 4: Arm 2: MZL, MCL and CLL Dose-finding**

**Figure 5: Arms 3 and 4 – Dose Expansion**

### 3.1.4 Dose-Limiting Toxicity

Dose limiting toxicities (DLTs) will be assessed during the venetoclax dose-finding for Arms 1 and 2 as follows:

- the first 4 weeks of triplet combination therapy for patients enrolled in Arm 1, Cohort 1 (C1D1 to C1D28)

- the first 5 weeks after starting venetoclax in Arm 2, Cohort 2 (C1D1 to C1D35).

Dose reductions of magrolimab and obinutuzumab are not permitted during DLT assessment period.

A DLT for this study is defined as any grade 3 or higher adverse event that is clinically relevant and deemed probably or definitely related to any of the study drugs or to the combination therapy, in the opinion of the Principal Investigator and occurs during the venetoclax dose-finding period with the exception of following:

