#### 3.1.4.1 Non-hematologic AEs

- Grade 3 nausea, vomiting, or diarrhea that persist  $\leq$  7 days with supportive care
- Grade 3 fatigue with improvement to  $\leq$  grade 2 within 7 days
- Grade 3 infection that improves to  $\leq$  grade 2 after initiation of antimicrobials
- Grade 3 electrolyte disturbances that improve to  $\leq$  grade 2 within 72 hours with appropriate medical management and are not associated with other clinically significant consequences.
- Grade 3 magrolimab- or obinutuzumab-infusion reactions that resolve to  $\leq$  grade 1 within 24 hours. **NOTE:** In a patient, if it is not clear if the AE is an infusion-related reaction (IRR), the patient may be replaced.
- Other grade 3 laboratory abnormality that is asymptomatic and deemed by the investigator to be not clinically significant

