### 3.1.5 Safety Ramp-Up of Venetoclax

Patients with FL (Arms 1 and 3; Cohorts 1 and 3) will start venetoclax at target dose for that particular dose level.

Intra-patient dose escalation of venetoclax will be performed with fixed doses of magrolimab and obinutuzumab for patients with MZL, MCL and CLL (Arms 2 and 4; Cohorts 2, 4, 5 and 6) during Cycle 1 (**Table 10**). If tolerated, venetoclax will be administered at the target dose level once daily for all subsequent cycles.

**NOTE:** During safety ramp-up, an individual patient who experiences a DLT or toxicity that meets DLT criteria during dose expansion (serious toxicity) can have venetoclax dose reduced to the dose of venetoclax that was tolerated and continue treatment (**Table 10**), if felt to be in the best interests of the patient. Once DLT assessment is complete, all dose modifications during safety ramp-up will be conducted per Sections **3.3.2** and **3.3.3**. DLT rules apply to all arms.

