#### **3.3.1 Exceptions to Dose Modifications/Delays during DLT Evaluation Windows**

##### **3.3.1.1 During venetoclax dose-finding (addition of venetoclax to magrolimab and obinutuzumab)**

Dose delays of magrolimab and obinutuzumab should be avoided during the DLT assessment (i.e., Cycle 1 of triplet combination therapy in Arms 1 and 2) to allow for identification of toxicities. If a patient experiences a DLT to triplet combination therapy, then all study therapy should be held for up to 2 weeks per the investigator. If DLT resolves and it is deemed safe to re-initiate therapy, then magrolimab and obinutuzumab should be re-started at the prior dose, and venetoclax should be re-started at one dose level lower. Dose levels for venetoclax dose modifications are mentioned in the table below ([Table 15](#)).

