#### 4.1.2.3 For any occurrence of laboratory TLS:

- Withhold the next day's venetoclax dose. If resolved within 24 to 48 hours of last dose, resume at the same dose.
- For any blood chemistry changes requiring more than 48 hours to resolve, resume at a reduced dose.
- For any events of clinical TLS, resume at a reduced dose following resolution

In addition to the above, additional recommendations for patients with chronic lymphocytic leukemia/ small lymphocytic lymphoma receiving first dose of venetoclax:

- For potassium increase  $\geq$  0.5 mmol/L from baseline, AND  $>$  5.0 mmol/L, recheck potassium, phosphorus, uric acid, calcium, and creatinine and follow guidelines per Section **4.1.2.2.1**
- For phosphorus increase of  $>$  0.5 mg/dL AND  $>$  4.5 mg/dL, administer phosphate binder and recheck potassium, phosphorus, uric acid, calcium, and creatinine.

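### No minimum Cycle 1 exposure is required for a patient to count as DLT-evaluable, so substantially under-dosed patients without a DLT tilt the 2-of-6 rule towards accepting the dose

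*Combined protocol and SAP*

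**What the plan says.** Each dose-finding cohort treats six patients at a venetoclax dose level. Under Table 8, with fewer than 2 DLTs in six, "This target dose will be used in expansion phase". With 2 or more at dose level 1, six patients enter at dose level (-1). The DLT window is 28 days in Arm 1 and 35 days in Arm 2 (section 3.1.4).

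A patient can leave the six in two ways:
- Section 3.1.1: "Patients who withdraw before completing DLT assessment for reasons other than a DLT, will not be evaluable for assessment of DLT", with replacement.
- Section 3.1.4.1: "In a patient, if it is not clear if the AE is an infusion-related reaction (IRR), the patient may be replaced".

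Neither is a test of exposure. The only toxicity population, in section 10.3.1, asks for a single dose of any study drug.

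On dosing inside the window, section 3.1.4 bars reductions of the two antibodies. Section 3.3.1.1 says "Dose delays of magrolimab and obinutuzumab should be avoided during the DLT assessment", without stating what a delay does to evaluability. For laboratory TLS, section 4.1.2.3 withholds venetoclax. It resumes at the same dose if the event resolves within 24 to 48 hours; otherwise "For any blood chemistry changes requiring more than 48 hours to resolve, resume at a reduced dose".

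**The concern.** A DLT-free patient is evidence about a dose only to the extent that the patient received it. The plan's own provisions can reduce Cycle 1 exposure without producing a DLT:

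- **Infection.** Section 3.1.4.1 exempts a Grade 3 infection that improves to Grade 2 or lower on antimicrobials. Section 3.4.2.5 holds the next magrolimab dose until a serious infection has clinically resolved. Table 11 schedules only four magrolimab doses in Cycle 1.
- **Blood chemistry.** Section 4.1.2.3 reduces venetoclax when changes last beyond 48 hours. Section 3.1.4.1 exempts Grade 3 electrolyte disturbances that improve within 72 hours. An event lasting between 48 and 72 hours may therefore lower the dose without counting as a DLT.
- **Missed tablets.** The venetoclax diary is optional (section 3.2), and no number of missed doses affects evaluability.

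The limits on antibody changes do not extend to venetoclax, the drug whose dose is being chosen. What is at stake is a single accept-or-reduce decision on six patients, after which up to 42 expansion patients receive the accepted doses (section 10.2).

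**Working it through.** **The plan's own figures.** Dose-finding: 2 cohorts × (6 at level 1 + 6 at level -1) = 24. Expansion: 18 + 6 + 12 + 6 = 42. Total: 24 + 42 = 66. The ceiling of 76 leaves 76 − 66 = 10 places. These agree with section 10.2. The plan states no target DLT rate and no operating characteristics for the 2-of-6 rule, so there is no stated probability to reproduce.

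**Time at target dose inside the window** (Tables 10 and 11):
- Arm 1: from Day 1. "Patients with FL (Arms 1 and 3; Cohorts 1 and 3) will start venetoclax at target dose for that particular dose level".
- Arm 2, level 1 (400 mg): Days 29–35, which is 7 of 35 days.
- Arm 2, level (-1) (200 mg): Days 22–35, which is 14 of 35 days.

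The scope for having no time at target is therefore greatest in Arm 2 at level 1. If a hold of about a week pushed the remaining ramp-up steps back by the same time, the 400 mg step would fall outside the window. No section says how the ramp-up resumes after a hold, so this is conditional.

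**Effect on the rule.** With six fully exposed patients at DLT risk p:

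P(2 or more DLTs) = 1 − (1−p)^6 − 6p(1−p)^5.

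At p = 0.30: 1 − 0.118 − 0.303 = 0.580 (from unrounded terms).

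Suppose k of the six carry a lower risk q. The DLT count is then a sum of independent Bernoulli variables, 6−k at risk p and k at risk q. I take q = p/2 and q = 0. For p = 0.30:
- k = 1, q = 0: 1 − 0.7^5 − 5(0.3)(0.7^4) = 1 − 0.168 − 0.360 = 0.472.
- k = 1, q = 0.15: 1 − [0.85 × (0.168 + 0.360) + 0.15 × 0.168] = 0.526.
- k = 2, q = 0: 1 − 0.7^4 − 4(0.3)(0.7^3) = 1 − 0.240 − 0.412 = 0.348.
- k = 2, q = 0.15: 0.468, by the same method.

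Neither p nor k is in the documents, so the range is shown.

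| Assumed p | All six fully exposed | One at p/2 | One at 0 | Two at p/2 | Two at 0 |
|---|---|---|---|---|---|
| 0.10 | 11% | 10% | 8% | 8% | 5% |
| 0.20 | 34% | 30% | 26% | 26% | 18% |
| 0.30 | 58% | 53% | 47% | 47% | 35% |
| 0.40 | 77% | 71% | 66% | 65% | 52% |
| 0.50 | 89% | 85% | 81% | 80% | 69% |

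Entries are the chance that the rule rejects the dose. Each lower-risk column is below the fully exposed one at every p, so the shift is always towards acceptance.

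**The case against.** The best case against the point has five parts.

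1. *The two exits may cover more than they seem to.* Section 3.10.1 speaks of withdrawal from protocol therapy, so a patient who stops treatment in Cycle 1 may already be replaced. This stands in part: section 3.1.1 does not say which withdrawal it means, and a patient who is interrupted and continues remains uncovered. A reader might infer that withdrawal is the only exit. Section 3.1.4.1 shows that it is not, although its exit is optional, has no exposure test and could remove a possible DLT.

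2. *Cycle 1 is protected.* Antibody delays are discouraged, antibody reductions are barred, and the triplet-phase hold rules in Tables 16 and 17 are labelled as applying after DLT assessment. This limits how often the problem arises. It does not say what happens to evaluability when it does, and it leaves the TLS and infection provisions in place.

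3. *The TLS route is narrow.* A reader might infer that any interruption keeps a patient below target to Day 35. The documents do not support that: a short hold resumes at the same dose, Arm 1 starts at target, and Arm 2 at level (-1) is due at target from Day 22. Longer TLS events may themselves be DLTs. The background sections give TLS rates of 3/106 in NHL with venetoclax, all laboratory and without dose interruption, and 3/212 with venetoclax plus obinutuzumab in CLL. At those rates two or more cases in six has probability of about 1.1% and 0.3%. At the 10/56 seen in the early CLL escalation it is about 29%. Two under-exposed patients from TLS alone is therefore unlikely unless that early rate applies. TLS is, however, only one of the routes.

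4. *Zero risk is an extreme.* All three drugs start on Day 1 or 2, and a DLT may relate to any of them. This stands; the zero columns are bounds.

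5. *Later safeguards exist.* The study-wide stopping rules in section 10.2 continue throughout. They mitigate a wrong acceptance but do not correct the dose decision.

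**Conclusion.** The gap is real and worth closing as a cheap improvement. Apart from withdrawal and optional replacement for an unclear infusion reaction, nothing ties DLT evaluability to the treatment received, and counting under-exposed patients as DLT-free favours acceptance. That they count as DLT-free follows from applying section 3.1.1 as written; no sentence states it.

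The size is illustrative. At an assumed 30% DLT risk, wrongful acceptance rises from 42% to 47%–53% with one patient at half or no risk, and to 53%–65% with two. Half risk means p/2 and patients are taken as independent. The number affected could be zero. A reader might infer that the design is likely to carry an unsafe dose forward. The documents do not show that, because they give neither a true DLT rate nor an expected frequency of interruption.

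**What to change.** In section 3.1.1, with a matching entry in section 10.3, define a DLT-evaluable set for the dose decision:
- every patient with a DLT in the window, whatever the exposure; and
- DLT-free patients who received a prespecified minimum share of planned Cycle 1 doses of each drug, including, in Arm 2, a stated minimum time at the target dose.

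The sponsor should set the thresholds. For DLT-free patients below them:
- if the shortfall was not due to study-drug toxicity, replace the patient;
- if it was due to study-drug toxicity, do not replace. Report the patient and consider the case explicitly in the dose decision.

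The second branch matters. Replacing everyone who missed an infusion or did not reach target would remove patients held back by toxicity short of a DLT and push the rule the same way as the present gap. The same edit should say whether withdrawal in section 3.1.1 means from the study or from protocol therapy.

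This changes who is counted, not how anyone is treated. The cost is a short paragraph and possibly a few replacements. They would draw on the 10 places between 66 and 76, which are shared with screen failures and other inevaluable patients across the whole study. Each would also add a further 4- or 5-week DLT window under the limit of two patients in assessment at a time.
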